The baseline demographic, primary and secondary outcome data that we are collecting as part of the NOBRO study is already routinely collected on patients within the hospital as part of the course of routine clinical care for patients with bronchiolitis.

Information collected about participants for the study will be used in order to report on outcomes. The data collected will be recorded on paper (as part of the NOBRO study source document) and will remain confidentially within the child's physical patient file. This information in these source documents will be in the form of grouped data, with no identifying information. Data for all patients entering the study will be deidentified and will thus exist as re-identifiable (coded) information. The baseline characteristics and subsequent outcome data measures of infants in each group will not reveal any personal details that threaten the identity or safety of any of the patients

Confidentiality will be maintained by having as few people as possible being able to access the data, prior to merging. Following merging, identifiable data shall be made de-identifiable. In the dissemination of results, only grouped data will be reported. If publicised only de-identified cases will be reported.

Measures to prevent misuse and loss involve storing data on a password protected computer file on the principal researcher's computers and on a transportable flash drive (for back up and future data storage purposes) that will remain in a locked filing cabinet, in the principal researcher's office when not in use. The transportable flash drive shall only be utilised when identifiers have been removed. The primary and secondary database managers shall manage the security of this device.

The results of the research will be disseminated in the following manner:

- In a report to the districts' Human Research Ethics committee
- At > or = 1 health conference
- Submitted to a peer-review journal for publication
- Participants in the study will be provided with a website link in which a simplified version of the study's results can be viewed.
- To fulfil a Royal Australasian College of Physicians training requirement of the primary investigator ([name])

Following the implementation of the study, the information gathered will be used to provide baseline data to substantiate further expansion and integration of the study to other wards and specialist services who care for patients with bronchiolitis requiring nasogastric fluids.

Information collected from the study will be disposed of 5 years after the youngest patients' 18th Birthday. Any electronic records relating to study data will be deleted and paper records will be placed into appropriately labelled shredding bins

I. Data Analysis and Statistical Considerations

No formal hypothesis testing will be completed, as this is a pilot study. Descriptive statistics will be used to measure the various outcomes of the trial- e.g. data completeness, % eligible patients approached, % eligible patients approached who then consented, total number of eligible patients per week. Data analysis will be done using Microsoft Excel in consultation with the biostatistician.

Data analysis in this pilot study will primarily be related to determining an appropriate sample size and analysis methods for the subsequent RCT. Data will be collected over a 2 month period during which we anticipate to recruit 30 participants based on the current bronchiolitis presentation rate.

The primary outcome measure will be time to adequate oral feeding (TAOF) as detailed above. Descriptive and graphical statistics will be used to ascertain the nature of the frequency distribution of TAOF. Understanding the nature of the distribution of TAOF will inform the most appropriate analysis method to be used in the RCT. If the distribution is normal, or can adequately be transformed to normality, the standard deviations (SDs) of TAOF in each treatment group along with means will be calculated. The SD estimates may then be used to estimate the sample size required in the RCT. The other requirement for this sample size estimation is an understanding of what the minimal clinically important difference (MCID) in TAOF is. As this is a new and specific measure, clinical members of the team will use this preliminary TAOF data to determine a consensus MCID for TAOF. Given this information, preliminary analyses will be undertaken to detect any difference, if any, in TAOF.

Similar analyses will be undertaken with respect of secondary objectives, hospital length of stay, and tolerability though these will not inform sample size. With respect to tolerability, this preliminary data will be used to assess possible tolerability indices that may be used in the main RCT.

At the end of the pilot, a qualitative judgement will be made by all investigators as to whether the it is appropriate to proceed, in line with Abbott $(2014)^{23}$:

- Insurmountable problems with necessary processes: stop
- Problems identified are surmountable: modifications will be necessary in full study protocol, and further pilot testing may be necessary
- Few or no major problems: a full study can proceed without modifications or further testing

4. Translation to Changes in Clinical Practice

To date, there have been no studies in patients with bronchiolitis to assess which nasogastric fluid regime (intermittent bolus or continuous nasogastric fluids) leads to a quicker return to oral feeding and a shorter duration of inpatient stay.

The NOBRO study will be the first of its kind to directly compare nasogastric fluid practices in patients with bronchiolitis. We hope that the study will help guide clinicians when determining what nasogastric fluid to prescribe for patients with bronchiolitis. We also hope that the results of the study will help supplement best practice guidelines used by our hospital with regards to the management of patients with bronchiolitis. We also hope that this research will help to inform clinicians working in other hospital and health settings and perhaps generate similar research trials.

We hope that this pilot trial will help us determine the following before proceeding with a larger scale randomised control trial:

- The validity of our research methods and primary outcome.
- Any barriers to proceeding with a larger scale randomised control trial.
- Preliminary data to assist with a power calculation for the larger scale randomised control trial

5. Timeline

After ethics and governance approvals, we aim to then start regular education sessions and awareness campaigns for the study for nursing, medical and administration staff over the following month.

We aim to start recruiting patients in January 2020 and aim to continue recruiting patients for the following 2 months.

After outcome data has been collected, we aim to collate our results, perform statistical analyses and report data outcomes over the following 2 months.

After analysing and reporting on the results of this pilot trial, we hope to proceed with running a larger, high powered randomised control trial to run for likely 18 months in duration.

6. Funding and Resources

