- The quality improvement study by Srinivasan et al aimed to hydrate patients with formula or breast milk via the nasogastric tube but found that the majority of patients were given Pedialyte (60%) compared with breast milk or formula (40%).
- The pilot study by Sammartino et al. (2002) describes using either gastrolyte or milk for patients receiving nasogastric fluids⁵.
- Patients receiving nasogastric fluids in the randomized control trial by Oakley et al. received continuous oral electrolyte solution for the first 2 hours of therapy, followed by 1-2 hourly boluses of expressed breast milk or formula³.
- It is difficult to determine the incidence in previous studies of patients receiving oral feeds whilst simultaneously receiving nasogastric fluids. The study by Kugelman et al. has openly disclosed that patients were allowed comfort, non-nutritive sucking for infants whilst receiving nasogastric fluid therapy¹³.
- Both Local and international bronchiolitis guidelines suggest the use of either formula or expressed breast milk delivered either continuously or via intermittent boluses every 2nd to 3rd hour^{6,19}.
- Local guidelines suggest that the ideal volume of nasogastric fluids to maintain hydration should be 60 to 100% of maintenance fluid to prevent complications secondary to the syndrome of inappropriate ADH secretion (SIADH)¹². This is similar to guidelines reported in other states⁴ as well as used in previous studies^{17, 20}.

Although clinical practice guidelines and pre-existing evidence support the use of nasogastric fluids for patients with bronchiolitis, there is no consensus as to which nasogastric fluid regime should be prescribed for patients with bronchiolitis.

Both clinically, and as seen in previous studies, there are two main regimes for nasogastric fluids; intermittent bolus fluids or continuous fluids.

- Intermittent bolus fluids refers to when a patient has the same volume delivered through the nasogastric tube over a 1 hour period that they would typically have in a normal oral feed.
- Continuous fluids refers to when a patient has the same bolus fluid amount delivered through the nasogastric tube, however given at a slow continuous rate.

However, there is no consensus as to which nasogastric fluid regime should be prescribed for patients with bronchiolitis.

Anecdotally, there exists clinical equipoise, and the decision of which nasogastric fluid regime to use for patients with bronchiolitis is usually clinician dependant.

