A local bronchiolitis guideline suggests that gastric distension from bolus feeds can result in worsening of respiratory symptoms, thereby suggesting the use of continuous nasogastric fluids in severe bronchiolitis. However, there is no evidence of previous studies supporting or refuting this practice within this guideline⁶.

Conversely, some clinicians hypothesise that delivering nasogastric fluids via intermittent boluses is more physiologically similar to an infant's normal pre-morbid oral feeding practices and could thus improve an infants' readiness to tolerate normal oral feeding during their course of bronchiolitis..

We look to investigate in infants less than 12 months of age with bronchiolitis that require nasogastric fluid therapy, which nasogastric fluid regime (continuous fluids or intermittent bolus fluids) leads to the patient having a quicker return to normal oral feeding, as well as a range of other secondary outcome measures.

We plan to conduct a randomised controlled trial (RCT) to help inform our hypothesis. Prior to this however, we will conduct a pilot RCT, in order to test and refine the study procedures prior to beginning the main trial and to identify what might be considered a clinically important difference in our primary outcome measure and its standard deviation. This will enable reliable power calculations for the proposed RCT. The primary outcome measure is a specifically defined measure of time taken for the patient to return to adequate oral feeding. As this is not a routine or well published measure, our pilot will enable a greater understanding of it and enable assessment of its appropriateness prior to the RCT. Other feasibility related factors will also be addressed such as recruitment and retention rates, possible problems in the randomisation process, and adherence to the randomised protocol.

Trials of a similar nature to this study were not found in The Australian New Zealand Clinical Trials Registry (ANZCTR) or in the US National Library of Medicine Clinical Trials Catalogue.

2. Study Objectives

a. Research Question and Aims/objectives

Population

• Patients less than 1 year (ie. Up to 364 days) old with a clinical diagnosis of bronchiolitis that have been assessed as requiring nasogastric fluids due to poor feeding and/or dehydration

Interventions

• The use of intermittent bolus nasogastric fluids (of either breast milk, formula or oral rehydration solution) every 3 hours

Comparator

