If consent is received, the patient will then be randomised to receive their nasogastric fluids at either a continuous rate or via intermittent boluses.

A block randomization strategy will be employed using the ralloc command of the statistical software Stata 15. Randomizations will be provided in consecutively numbered opaque sealed envelopes.

Blinding and allocation concealment

Due to the nature of the interventions assigned to each group, blinding of participants and the research assistant is not feasible. However, once outcome data is collected and recorded by the research assistant, the final data set will be further coded in such a way as to deidentify which nasogastric fluid regime patients were assigned to, further ensuring that the statistician analysing the results is blinded to the patients allocation .

e. Consent

Due to the age of patients in the trial, consent will need to be obtained from the patients' parent/s or guardian.

A dedicated research assistant will be responsible for providing the study consent and information form to eligible patients, as well as obtaining consent to minimise any conflicts of interest. However, in cases where the decision to initiate nasogastric fluids occurs when the research assistant is not available (such as after-hours), this role will be performed by the patient's treating clinician or nurse.

We will mitigate the risk of coercion by providing clinical staff with training around consenting procedures for the trial, ensuring that parents and guardians will be made aware that participation in this study is completely voluntary and that refusal to participate or withdrawal from the study will not affect their child's clinical care in any way.

The information sheet provided to parents/guardians will encompass a simplified lay version of the current evidence regarding nasogastric fluid therapy in bronchiolitis, the purpose of the NOBRO study and its' methodology. The information leaflet will specify our hospitals practice regarding the use of nasogastric fluids in patients with bronchiolitis, and that all patients within the study will be managed in line with best practice as noted by the PREDICT Australasian Bronchiolitis Guideline¹². The information sheet will also contain important information regarding patient confidentiality and disclosure of information. The information sheet will also include contact details of the investigating team and the hospitals Ethics association.

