 - Episodes of vomiting will be detected and documented by nursing staff looking after the patient in their medical chart as part of the patient's Fluid Balance. This is no different to the standard of care which is already instituted across our hospital for patients with bronchiolitis.
 - o If vomiting occurs, the patients treating nurse will cease the patients' nasogastric fluids and generate a medical officer review. Once a medical review has occurred, a clinical decision will be made as to whether nasogastric fluids should be re-started, whether an alternative form of hydration should be trialed (such as oral or intravenous fluids),

or any other medical care that should be undertaken. The management applied will be recorded in the patients' medical chart and will be reported as part of the trial.

- Pulmonary aspiration of nasogastric fluids
 - o Defined as inhalation of liquids into the lung²².
 - Episodes of aspiration will be graded as per the CTCAE²².
 - Grade 1: Asymptomatic; clinical or diagnostic observations only; intervention not indicated
 - Grade 2: Altered eating habits; coughing or choking episodes after eating or swallowing; medical intervention indicated (e.g., suction or oxygen)
 - Grade 3: Dyspnea and pneumonia symptoms (e.g., aspiration pneumonia);
 hospitalization indicated; unable to aliment orally
 - Grade 4: Life-threatening respiratory or hemodynamic compromise; intubation or urgent intervention indicated
 - Grade 5: Death
 - Episodes of aspiration will be detected and documented by nursing staff looking after the patient in their medical chart. This is no different to the standard of care which is already instituted across our hospital for patients with bronchiolitis.
 - o If a pulmonary aspiration event occurs, the patients treating nurse will cease the patients' nasogastric fluids and generate a medical officer review. Once a medical review has occurred, a clinical decision will be made as to whether nasogastric fluids should be re-started, whether an alternative form of hydration should be trialed (such as oral or intravenous fluids), or any other medical care that should be undertaken. The management applied will be recorded in the patients' medical chart and will be reported as part of the trial.
- If the patient has a worsening of their respiratory status believed to be secondary to their nasogastric fluid regime

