 - We have defined this adverse event as when a patient experiences a sudden increase in any of the following that occurs persistently during, or within an hour after the patients nasogastric fluid regime has commenced
 - Heart rate >20 above baseline
 - Respiratory Rate > 10 above baseline
 - Work of breathing
 - Oxygen requirement

Both nasogastric fluid regimes are essentially treatment as usual, so we expect that the study as a whole poses no foreseeable additional risk to patients. We will still perform safety analysis on the pilot data collected.

We do not anticipate any significant difference in safety between the interventions. If we do detect a significant difference in safety, we will have procedures in place to address this for the subsequent larger study.

There is no evidence in the literature to suggest that patients receiving nasogastric fluids are at risk of a serious adverse event (SAE), such as

- death during the study period
- electrolyte disturbance causing seizure
- Any other event not mentioned above that is life threatening or jeopardises the patient or requires medical or surgical intervention

We will endeavour to manage any serious adverse events with the following practice:

- SAEs need to be reported within 24 hours by telephone to the local site investigator.
- The local investigator must report the SAE to their local ethics committee within 48 hours (or in accordance with local ethics committee regulations).
- The local investigator must also report SAEs to the principal investigators who will report the event to the Data Monitoring Committee chairman.
- The principal investigator will also report the SAE to all Ethics Committees and other regulatory bodies involved in the trial as per regional regulatory requirements.
- SAEs will also be reported to the consultant of the child's treating team. The medical consultant will initiate appropriate management and inform the family if the family is not already aware of the event. This reporting is the responsibility of the site investigator

g. Participant Withdrawal Procedures

Parents/guardians of any patient enrolled in the trial are able to withdraw their consent at any point after it is initially obtained either verbally or through written means. At the point of withdrawal of consent, the treating clinician will determine the course of ongoing therapy for the patient in discussion with the patients' parent/guardian as per normal practice.

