After the patient has been randomised to receive either continuous or intermittent bolus nasogastric fluids, the treating nurse will inform the treating medical doctor to prescribe the appropriate fluid type (oral rehydration solution, breast milk or formula) and rate (based on their randomisation group, weight and expected total fluid quota¹).

Patients assigned to the Intermittent bolus nasogastric fluid group will receive their fluid 3 hourly intervals based on their age and weight over 1 hour via a pump.

The fluid quota that is prescribed to each patient will be as per our local bronchiolitis guideline⁶.

- o Patients aged 0-3 months will receive nasogastric fluids at a rate of 150ml/kg/day
- o Patients aged 3-6 months will receive nasogastric fluids at a rate of 120ml/kg/day
- o Patients aged 6-12 months will receive nasogastric fluids at a rate of 100ml/kg/day
- O Due to the risk of fluid overload and the Syndrome of Inappropriate Anti-Diuretic Hormone (SIADH) in patients with bronchiolitis, patients will be prescribed nasogastric fluids at 2/3 (67%) of the fluid quotas stated above. This is as per recommended practice by the Australasian Bronchiolitis Guideline.³

The treating nurse will then initiate the prescribed fluid regime.

Patients in the study will have their nasogastric fluids ceased when they have achieved adequate oral feeding, or if determined by the treating clinician if an adverse event related to the nasogastric fluid regime occurs.

In our study, Adequate oral feeding has been defined by as when the patient tolerates two consecutive feeds of > 50% of their normal pre-morbid oral feed quotas.

- For patients that are normally formula-fed, we will be able to quantify when the patient has >50% of their normal pre-morbid oral feed quotas
- For patients that are normally breast-fed, we will assume that the patient has achieved adequate oral feeding when they have achieved two consecutive breastfeeds, each of which has lasted for >50% of their normal pre-morbid breastfeed duration.

There may be occasions where there is a clinical need to deviate from this protocol. For example;

 A patient experiences an adverse event and the medical officer deems it necessary to either change or cease the patients nasogastric fluid regime; or

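### The respiratory adverse event depends on unblinded staff attributing it to the regime, and its time window is ambiguous, so recorded incidence can differ between arms at equal true risk

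*Protocol*

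**What the plan says.** Section 3.f (Risk Mitigation Procedures) names the event as a "worsening of their respiratory status believed to be secondary to their nasogastric fluid regime". The definition beneath it asks for a sudden rise in heart rate (more than 20 above baseline), respiratory rate (more than 10 above baseline), work of breathing or oxygen requirement that "occurs persistently during, or within an hour after the patients nasogastric fluid regime has commenced". The last two criteria have no threshold.

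The causal element appears twice more. The synopsis lists the main-trial outcome as worsening secondary to the fluids, and section 3.i (Outcome Measures) lists adverse events that may be attributed to the fluids, with respiratory worsening among them.

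On delivery, section 3.h (Allocation) says bolus infants "will receive their fluid 3 hourly intervals based on their age and weight over 1 hour via a pump", while the Background describes the comparator as "given at a slow continuous rate". On masking, section 3.d says "blinding of participants and the research assistant is not feasible"; only the statistician is masked, after outcomes have been recorded. On prior expectation, the Background reports a local guideline suggesting that "gastric distension from bolus feeds can result in worsening of respiratory symptoms". Section 3.h takes the fluid quotas from that same guideline.

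**The concern.** Two features of the definition can make ascertainment depend on the arm.

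The first is attribution. If an event counts only when it is "believed to be secondary to their nasogastric fluid regime", the count measures both how often infants deteriorate and how readily staff blame the fluids. Staff know the arm and work under a guideline that links boluses to respiratory worsening, so the second component can differ between arms. Masking the statistician later cannot correct a judgement already made at the bedside.

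The second is the window. It is tied to the *regime*, and the text does not say whether that means the whole course or each delivery of fluid.

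Adverse-event incidence is a stated pilot outcome. Section 3.f promises a safety analysis and says that a significant safety difference would lead to procedures for the larger study. If ascertainment differs by arm, neither a difference nor its absence can be read as evidence about the regimes. An analysis plan cannot recover events that were never recorded as events.

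**Working it through.** The protocol gives no respiratory event rate, so there is no figure to reproduce. The checks below ask what would be recorded if the true risk were identical in both arms.

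**Inputs from the protocol**
- Bolus delivery: 1 h in every 3 h, so 24/3 = 8 boluses and 8 × 1 h = 8 h a day (section 3.h).
- Continuous delivery: taken as 24 h a day (Background).
- Sample size: 30 in total.

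**Assumptions, not in the protocol**
- True risk p of a qualifying worsening over the course: 10%, 20% or 30%, the same in both arms.
- Probability a that staff attribute a worsening to the fluids: several pairs.
- About 15 infants per arm, since no allocation ratio is stated.

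**1. Attribution alone (same window in both arms).** Recorded rate = p × a.

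| p | a, bolus / continuous | Bolus | Continuous |
|---|---|---|---|
| 20% | 80% / 80% | 0.20 × 0.80 = 16% | 16% |
| 20% | 90% / 60% | 0.20 × 0.90 = 18% | 0.20 × 0.60 = 12% |
| 20% | 90% / 30% | 18% | 0.20 × 0.30 = 6% |
| 30% | 90% / 60% | 27% | 18% |

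Equal attribution gives equal rates. Unequal attribution produces a difference that is not real.

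**2. Window alone.** Hours a day inside the window:
- Whole course: 24 h in both arms. The clause about the first hour is then redundant, because *during* already covers it.
- Each bolus, within an hour of its start: 8 h (bolus) against 24 h (continuous), a ratio of 24/8 = 3.0. A bolus lasts 1 h, so the hour after its start is the bolus itself.

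With a constant hazard and window share f, recorded bolus rate = 1 − (1 − p)^f. For f = 8/24 = 1/3:
- p = 10%: 1 − 0.90^(1/3) = 3.5%, against 10% continuous.
- p = 20%: 1 − 0.80^(1/3) = 7.2%, against 20%.
- p = 30%: 1 − 0.70^(1/3) = 11.2%, against 30%.

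These contrasts are upper limits for the per-bolus reading. The definition requires persistence, and a rise that starts between boluses and lasts would still be present at the next bolus, at most 2 h later.

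**3. Both together (p = 20%, attribution 90% / 60%).**
- Whole-course window: 18% bolus, 12% continuous.
- Per-bolus window: 7.2% × 0.90 = 6.5% bolus, 12% continuous.

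The sign of the difference changes with the reading of one word.

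**4. Scale in the pilot.** At 15 per arm, 18% against 12% is 2.7 against 1.8 events. The per-bolus window alone gives 15 × 0.072 = 1.1 against 15 × 0.20 = 3.0 events.

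**5. After the change.** With f = 1 in both arms and no attribution condition, equal true risk gives equal recorded risk: 20% and 20%.

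**The case against.** A reader might infer that the continuous arm is observed three times as long and that the safety comparison is therefore biased against it. The protocol does not support that. It uses *regime* for the assigned mode or the whole course: the Background speaks of two main regimes, and section 3.h says "The treating nurse will then initiate the prescribed fluid regime". On that usage the window is the same in both arms. The 3.0 ratio arises only if staff apply the definition to each bolus. A ratio of 1.5 (24 h against 16 h) would need *commenced* to be read as *ended*. What stands is that the wording is ambiguous and that the redundant second clause invites a per-bolus reading.

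On attribution, it can be said that the causal phrase is only a label and that the physiological criteria are the definition. Requiring a causal link also answers the protocol's own complaint that an earlier trial could not separate fluid effects from the illness. But the causal wording recurs in the synopsis and in section 3.i, and unblinded belief does not achieve that separation. It is fair to add that the guideline only suggests that boluses can worsen symptoms, that the protocol notes it offers no evidence, and that the Background describes equipoise. Staff expectation is therefore a plausible source of differential recording, not a demonstrated one.

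The consequence is also limited. The pilot is small and does no formal testing. Intensive care admission, oxygen duration, change to intravenous fluids, and type and duration of respiratory support are all collected without any causal condition.

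**Conclusion.** The attribution problem holds under either reading of the window: the event as defined can be recorded at different rates in the two arms when the true risk is the same. The window is ambiguous but not shown to be unequal: 24 h against 24 h a day on the reading the protocol's usage favours, 8 h against 24 h if applied per bolus. The two effects probably act in opposite directions, so the net direction is unknown. This is a risk of bias and not a demonstrated bias.

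The sizes shown (18% against 12% from attribution; up to 7.2% against 20% from a per-bolus window) rest on assumed risks, attribution probabilities, a constant hazard and about 15 infants per arm. In the pilot they amount to one or two events. The point matters mainly because the pilot exists to refine procedures, and this definition is intended for the main trial. It is a worthwhile, inexpensive improvement and no obstacle to running the pilot.

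**What to change.** In section 3.f, and correspondingly in section 3.i and the synopsis:

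- Remove the causal belief from the event definition and count every respiratory worsening that meets the listed criteria.
- Give work of breathing and oxygen requirement operational definitions, and state what baseline, sudden and persistent mean.
- Use one observation period and one observation schedule in both arms, from first start of nasogastric fluids to a common endpoint, whether or not the pump is running. The endpoint should not be the end of nasogastric fluids, because time on fluids is expected to differ by arm. A fixed number of hours from first start, chosen by the team, would serve.
- Report per infant and per 24 h observed, so that infants discharged or transferred early are handled openly.
- Record believed causality as a separate, secondary field on the bedside form.

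The cost is protocol wording, one extra field and some staff training. The change concerns counting only and leaves the clinical response to a worsening infant untouched. The downside is that more natural-history events will be counted in both arms, which dilutes any regime-specific signal; the separate causality field keeps that information available.
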